13 RISK-BENEFIT ANALYSIS

13.1 ANTICIPATED CLINICAL BENEFITS

The TearCare™ System will be performed with the aim of increasing tear break up time and improving meibomian gland function. The anticipated clinical benefit of these improvement is relief of the subjects' dry eye symptoms. The goal of the procedure is to provide a safe, reproducible, and practically feasible treatment for dry eye disease. Additionally, performing the procedure under the direct supervision of a trained corneal specialist further ensures the safety and proper delivery of therapy.

13.2 ANTICIPATED ADVERSE DEVICE EFFECTS

Anticipated adverse effects associated with the TearCare System have been described above in Section 12.2.

13.3 RESIDUAL RISKS ASSOCIATED WITH THE INVESTIGATIONAL DEVICE, AS IDENTIFIED IN THE RISK ANALYSIS REPORT

Sight Sciences believes that there are no Intolerable residual risks from this fully non-invasive, controlled heat treatment device that can be easily and quickly removed from the patient by the supervising ophthalmologist.

13.4 RISKS ASSOCIATED WITH PARTICIPATION IN THE CLINICAL INVESTIGATION

As with any type of eye procedure, there are potential risks that are associated participating in the investigation including:

- Post-procedure Discomfort
- Blurred Vision
- Inflammation of eyelids

In addition, subjects who are asked to discontinue pre-procedure dry eye medications may note that their eyes feel drier. All anticipated study risks are listed in Section 12.2.

13.5 POSSIBLE INTERACTIONS WITH CONCOMITANT MEDICAL TREATMENTS

It is anticipated that there will be no interactions with concomitant medical treatments.

13.6 STEPS THAT WILL BE TAKEN TO CONTROL OR MITIGATE THE RISKS

The major risks to the subjects and the steps taken to control or mitigate them are described below:

1. Overheating of the eyelids: All TearCare treatments will be done in the investigator's office under direct supervision of the investigator. The device delivers heat to the eyelids at a temperature ranging from 41-45°C. This temperature range was selected because it is both safe for eyelid heating and effective for melting obstructions in the meibomian glands.^{33,34,35,36} The user can adjust the temperature up or down to a level that is comfortable and may also

shut off the System at any time if it is too uncomfortable or painful. In addition, the TearCare System continuously monitors and regulates the temperature at the tissue-contacting surface of the iLid devices and has been designed to not exceed the maximum allowable temperature.

2. Corneal abrasion: If the iLid devices are not positioned properly or come loose during the treatment, there is the potential for a corneal abrasion. To mitigate this, the supervising physician will apply the strips to the subject and will monitor their position during the treatment to ensure they remain in place and secure.

In addition, there is the possibility of corneal abrasion or abrasion of the eyelid surface during expression of the meibomian glands. To reduce the chance of abrasion, the forceps have been designed with smooth surfaces (i.e. no rough edges) and only trained users will perform expression.

3. Worsening of dry eye symptoms: It is possible that subjects will experience a worsening of dry eye symptoms during the study. Subjects will undergo a complete eye exam at each visit and if any untoward or worsening signs of ocular surface disease are observed, they will be treated appropriately.

In addition to the above, the following mitigation steps have also been taken to reduce the risks in this study:

- The device has been tested to demonstrate that it meets performance and safety specifications, as described in Section 7.1.
- Instructions for Use are provided with each device.
- The ophthalmologist using the device is board-certified and has experience in how safely and correctly apply and remove the iLid devices, and operate the TearCare System.

13.7 RISK-TO-BENEFIT RATIONALE

The risks in this study are low, due to the non-invasive nature of the TearCare System. In addition, these risks are generally temporary and are readily treatable or reversible with no medical intervention or, in some cases, using standard medical treatment.

Against these low risks are the potential for a reduction in subjects' eye discomfort and symptoms due to dry eye syndrome. Reduction in dry eye symptoms holds the possibility of several related benefits to the subjects, including:

- Improved vision
- Improved productivity
- Reduced dependence on medications and lubricants while simultaneously improving physiologic tear production ("your own tears")

- Reduced costs to subjects to treat their dry eye symptoms

On the basis of this analysis, the potential benefits to subjects related to treatment with the TearCare System outweighs the relatively low risk associated with the System.

14 STATISTICAL CONSIDERATIONS

14.1 HYPOTHESIS

This pilot study is not a hypothesis-driven study.

14.2 SAMPLE SIZE CALCULATION

This is an extension of the original TearCare Pilot Study (Study # 05429). The sample size for this study is defined by the number of subjects who were enrolled in the TearCare arm of the pilot study (i.e. 12 subjects).

14.3 PASS/FAIL CRITERIA

No pass/fail criteria are defined for the study.

14.4 STATISTICAL DESIGN, METHOD & ANALYTICAL PROCEDURES TO BE USED

Only basic descriptive statistics will be used to analyze data from the study.

14.5 INTERIM ANALYSIS AND EARLY TERMINATION CRITERIA

No interim analysis or early termination criteria are planned for this study.

14.6 DEVIATION FROM THE STATISTICAL PLAN

Any deviations from the statistical plan will be noted in the final report.

15 MONITORING PROCEDURES

15.1 MONITORING TO BE CONDUCTED DURING THE INVESTIGATION

- Since [name] has already conducted dry-eye related clinical trials with Sight Sciences, no site qualification visit will be required.

- Sight Sciences personnel will meet with the investigator(s) and clinical study staff at the time the site begins to enroll in order to ensure that subjects are being properly selected and that study data are being correctly recorded.
- Sight Sciences personnel or designee will visit the clinical site periodically during the study to review and/or collect the Case Report Forms.
- At the conclusion of the trial there will be a study closure visit during which, the following items will be reviewed and actions performed:
 - A final inspection of the study binder
 - Accountability and return of all devices and study materials to the sponsor
 - Close-out notification to the IRB

15.2 EXTENT OF SOURCE DATA VERIFICATION

The study CRF will serve as both the source document and the CRF.

16 DATA AND QUALITY MANAGEMENT

All study-related data will be recorded on Case Report Forms. When subjects are enrolled in the study, they will receive a unique study identifier, which will be used to identify them on all Case Report Forms. The Enrollment log containing the subject identifying information and the subject study id will be maintained under the investigator's control at all times. No subject-identifying information will ever leave the site.

16.1 DATABASE MANAGEMENT

Data Management will be performed by Sight Sciences who will create a database or spreadsheet in which the study data will be entered. Sight Sciences will be responsible for tracking the receipt of CRFs and data corrections, data entry, and preparing data reports for statistical analysis.

16.2 RETENTION PERIOD

Clinical sites are to retain any and all clinical trial material (documentation, photographs, etc.) for a period of two years from the date the marketing application is approved or two years after the investigation has been discontinued and the FDA notified, or as directed by their institutional document retention requirements, whichever is the longest. After that time, the items must be returned to Sight Sciences for archiving. Unused medical devices are to be returned to the sponsor at the conclusion of the enrollment period.

17 PROTOCOL MODIFICATIONS AND DEVIATIONS

Protocol modifications may occur during the study. Each will be approved by the sponsor before implementation. Each will undergo Institutional Review Board (IRB) review and approval, as necessary.

Any deviations from this protocol intended to protect the life or physical well-being of a subject in an emergency are to be reported to Sight Sciences, Inc. as well as the IRB as soon as possible, and no later than 5 working days after the emergency occurred.

All protocol deviations will be documented using Protocol Deviation form.

18 DEVICE FAILURES AND MALFUNCTIONS

All device failures or malfunctions should be recorded on the Case Report Forms and reported to Sight Sciences Customer Service [contact]).

19 STATEMENTS OF COMPLIANCE

This study shall be conducted in accordance with the Declaration of Helsinki (Appendix B). The study shall not begin until approval has been obtained from the reviewing IRB. The investigator shall conduct this investigation in accordance with the signed agreement with the sponsor, the investigational plan, the IDE regulation and other applicable FDA regulations, and any conditions of approval imposed by an IRB or FDA.

20 STUDY ADMINISTRATION

20.1 DEVICE ACCOUNTABILITY

With each shipment of study devices, Sight Sciences will include a Packing List that will provide the items shipped. This packing list must be reconciled by the site with the contents of the shipment and then the contents of the shipment should be entered on the Device Accountability Log (this log is contained within the regulatory binder at the site). All study devices at the site must be stored in a secured/locked area. Device reconciliation activities will also be conducted periodically in conjunction with site monitoring visits.

The investigator must maintain accurate records of the receipt of all devices shipped by Sight Sciences, including the date and lot numbers received with the use of the device inventory tracking log. The use of devices will also be recorded.

20.2 EARLY TERMINATION OR SUSPENSION OF AN INVESTIGATION

If the study is terminated, subjects will be followed up in accordance with the normal standard of care and adverse events, if any, will be tracked. No other special procedures are necessary.

In the event that there are significant human use issues with the device, the investigator will be consulted to make a determination of whether the study should be terminated or not.

20.3 INVESTIGATOR RESPONSIBILITIES

20.3.1 GENERAL RESPONSIBILITIES OF INVESTIGATORS

An Investigator is responsible for ensuring that an investigation is conducted according to the signed agreement, the investigational plan and applicable FDA regulations, for protecting the rights, safety, and welfare of subjects under the Investigator's care, and for the control of devices under investigation. An Investigator also is responsible for ensuring that informed consent is obtained in accordance with 21 CFR part 50.

20.3.2 SPECIFIC RESPONSIBILITIES OF INVESTIGATORS

1. Awaiting approval - An Investigator may determine whether potential subjects would be interested in participating in an investigation, but shall not request the written informed consent of any subject to participate, and shall not allow any subject to participate before obtaining IRB approval.
2. Subject Qualification - The Investigator is responsible for ensuring that all subjects entering the study conform to the patient selection criteria.
3. Compliance - An Investigator shall conduct an investigation in accordance with the signed agreement with the Sponsor, the investigational plan, all applicable FDA regulations, and any conditions of approval imposed by an IRB or FDA.

20.3.3 INVESTIGATOR RECORDS

A participating Investigator shall maintain the following accurate, complete, and current records relating to the Investigator's participation in an investigation for the period specified in Section 16.2:

1. All correspondence with another Investigator, an IRB, the Sponsor, a monitor, or FDA, including required reports.
2. Records of each subject's case history and exposure to the device. Case histories include the study CRF's/worksheets and supporting data including, for example, signed and dated consent forms and medical records. Such records shall include:
 - a) Documents evidencing informed consent.
 - b) All relevant observations, including records concerning adverse device effects (whether anticipated or unanticipated), information and data on the condition of each subject upon entering, and during the course of, the investigation, including information about relevant previous medical history and the results of all diagnostic tests.
3. The protocol, with documents showing the dates and reasons for each deviation from the protocol.
4. Any other records that FDA requires to be maintained by regulation or by specific requirement for a category of investigations or a particular investigation.

20.3.4 INVESTIGATOR REPORTS

An Investigator shall prepare and submit the following complete, accurate, and timely reports:

1. Unanticipated Adverse Device Effects - An Investigator shall submit to the Sponsor and to the reviewing IRB a report of any unanticipated adverse device effect occurring during an investigation as soon as possible, but in no event later than 10 working days after the Investigator first learns of the effect.
2. Withdrawal of IRB Approval - An Investigator shall report to the Sponsor, within 5 working days, a withdrawal of approval by the reviewing IRB of the Investigator's part of an investigation.
3. Progress - An Investigator shall submit progress reports on the investigation to the Sponsor, the monitor, and the reviewing IRB at regular intervals, but in no event less often than yearly.
4. Deviations from the Investigational Plan - An Investigator shall document and report to the Sponsor any deviation from the investigational plan.

5. Informed Consent - If an Investigator enrolls a subject without obtaining informed consent, the Investigator shall report such use to the Sponsor and the reviewing IRB within 5 working days after the use occurs.
6. Final Report - An Investigator shall, within 3 months after termination or completion of the investigation or the Investigator's part of the investigation, submit a final report to the Sponsor and the reviewing IRB.
7. Other - An Investigator shall, upon request by a reviewing IRB or FDA, provide accurate, complete, and current information about any aspect of the investigation.

20.4 INVESTIGATOR AGREEMENT

The principal investigators in each center shall agree to the clinical protocol and any amendments and indicate their approval and agreement by signing and dating the Investigator Responsibility Agreement.

[figure not shown]
21 ASSOCIATED DOCUMENTS

[figure not shown]
The investigator should refer to the TearCare Instructions for Use for instructions in how to operate the study device.

22 PUBLICATION POLICY

[name], the Principal Investigator, may publish the data in a medical newsletter or ophthalmic journal.

[REDACTED]

24 APPENDIX A – METHODS FOR OCULAR EXAMS AND TESTS AND ADMINISTRATION OF QUESTIONNAIRES

24.1 EYE EXAM

A standard eye exam shall be performed, including slit lamp examination to look for the presence of erythema, conjunctival discharge, tear meniscus, thickening of the lid margins, and telangiectasia.

24.2 MEIBOMIAN GLAND ASSESSMENT

Meibomian gland assessment should be performed and the following should be scored:

- Total number of glands from which a fluid secretion can be expressed, regardless of qualitative appearance
- Quality of secretions scored per the scale:³⁷
 - 0 = nothing
 - 1 = toothpaste
 - 2 = cloudy
 - 3 = clear

From this scoring the following endpoints will be assessed:

- The number of Meibomian glands yielding clear liquid secretions
- The number of glands secreting any liquid (clear or cloudy)
- The total Meibomian Gland Score

24.3 TEAR BREAKUP TIME (TBUT)

TBUT is an indicator of tear film instability and detects dry eye syndrome due to evaporative causes such as meibomian gland disease.

To measure TBUT, instill fluorescein into the eye using 2% fluorescein solution prepared according to the method defined by Gyau et al.³⁸ Ask the subject to blink several times. Record the break-up time using a stopwatch. Repeat the test 3 times and take the average of the 3 measurements.

[figure not shown]
24.4 CORNEAL AND CONJUNCTIVAL STAINING

Corneal staining should be assessed immediately following TBUT measurements (i.e. within 1-4 minutes after instillation of fluorescein dye) to assure the dye does not diffuse into stroma, blurring the discrete margin of any staining defects. A yellow Wratten filter should be used to improve any visualization of corneal staining. Grade the corneal staining using the NEI/Industry Grading System provided below in Figure 1

[figure not shown]
Conjunctival staining: Prepare 1% lissamine green solution according to the method defined by Gyau et al.³⁹ Instill the dye into the lower conjunctival fornix. Wait at least one minute before grading the conjunctival staining. The conjunctival staining grading should be performed 1 minute after instillation of stain and within 4 minutes of staining. Perform a slit lamp exam to score the conjunctival staining per the NEI grading system shown above below in Figure 1. Start with a low illumination and increase the level until the lissamine green staining is most visible.

Figure 1: NEI/Industry Grading System for Corneal and Conjunctival Staining⁴⁰

Score each of 5 areas of the cornea and total score:

Score each of 6 areas of the conjunctiva and total score:

24.5 VISUAL ACUITY

Best spectacle-corrected visual acuity will be measured using the Snellen method.

24.6 SPEED QUESTIONNAIRE

The SPEED Questionnaire will be administered to the subjects in the doctor's office by either the study coordinator or the Investigator. A total SPEED score is calculated by adding the Frequency and Severity scores.

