6.3 INSTRUCTIONS FOR USE

Instructions for Use are provided with each TearCare System.

6.4 SUMMARY OF THE TRAINING AND EXPERIENCE NEEDED FOR USE OF DEVICE UNDER INVESTIGATION

This is a single-center study, conducted by [name]. [name] is a co-inventor of the TearCare System and is familiar with its proper use. He will review the Instructions for Use in advance of initiating the investigation.

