9 STUDY DESIGN

This is a prospective, non-randomized, single-center case series study. No specific attempts will be made for minimization of bias, such as blinding or masking.

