11.6 FOLLOW-UP VISITS

Prior to the Visit: Reminder Call

Since dry eye drops and lubricants can affect the endpoint assessments, it is important to call subjects a few days before their follow-up visits to remind them that on the day of the Follow-up visit, they should not to use any of these products before the Follow-up visit.

Order of Procedures During the Follow-Up Visit

Follow-up exams should not be performed by the clinician who performed the TearCare procedure.

A large block of text is completely redacted with black bars, representing a list of procedures or steps.

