24.7 OSDI QUESTIONNAIRE

The OSDI Questionnaire will be administered to the subjects in the doctor's office by either the study coordinator or the Investigator. The overall OSDI Total score (from 0-100) and scores for the three subscales will be totaled according to the OSDI instructions. Based on the recommended cutoffs for OSDI Total score, subject results are grouped as follows:

- Mild – 13-22
- Moderate – 23-32
- Severe – 33 or higher

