24.8 SANDE QUESTIONNAIRE

The SANDE is a simple dry eye instrument containing two items measuring the frequency and severity of symptoms, each was assessed on a 100 mm visual analog scale (VAS) ranging from 'Never/Very comfortable' to 'All the time/Very severe' and scored from 0 to 100. Refer to Figure 2.

A SANDE Total score (also ranging from 0 to 100) is calculated as the square-root of the product of the two item scores.

Based on the SANDE total score, subject results are grouped into three categories:

- Mild: <40
- Moderate: 40-50
- Severe: >50

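### SPEED and OSDI may be administered at any visit by the Investigator, a co-inventor who delivers the treatment, and the examiner rule in 11.6 does not on its wording reach questionnaires (minor, cheap to fix)

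*Combined protocol and SAP*

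**What the plan says.** **Who administers the questionnaires.** Section 24.6 has SPEED administered "by either the study coordinator or the Investigator". Section 24.7 says the same of the second instrument: "The OSDI Questionnaire will be administered to the subjects in the doctor's office by either the study coordinator or the Investigator". Neither section distinguishes baseline from follow-up. Section 24.8 names no administrator for SANDE; it describes two items marked on visual analog scales.

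**Who the Investigator is.** Section 6.4 says that the person conducting this single-center study "is a co-inventor of the TearCare System and is familiar with its proper use". Section 13.6 places all treatments "under direct supervision of the investigator", and section 6.5 has the investigator perform the manual gland expression after the heat session.

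**What separation exists.** Section 9 describes a non-randomized case series and adds: "No specific attempts will be made for minimization of bias, such as blinding or masking". Section 11.6 nevertheless contains one safeguard: "Follow-up exams should not be performed by the clinician who performed the TearCare procedure". Section 11.5.2, on the baseline visit, names exams, tests and questionnaires as three different things.

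**What the scores are used for.** Section 8.1 makes change from baseline in SPEED, OSDI and SANDE secondary effectiveness endpoints. The primary endpoint is change in TBUT at 4 weeks. A SPEED score of at least 6 is also an entry criterion (10.1).

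**The concern.** A patient-reported score can depend on who presents the form. A subject who has just been treated, knows it, and is handed the questionnaire by the person who treated her and helped invent the device may lean towards reporting improvement. If a different role gave the baseline form, any difference between the two administrators is added to the change score as well.

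There is no control arm to absorb either effect, so both would be reported as part of the response to re-treatment. Relief of symptoms is the benefit that section 13.1 anticipates, and the risk-benefit argument in 13.7 rests on it. The plan already accepts the principle for follow-up exams. Leaving questionnaires outside that rule keeps a source of bias that could be removed at little cost.

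**Working it through.** The plan gives no figure to reproduce here. It has no hypothesis (14.1), no pass/fail criterion (14.3) and only descriptive statistics (14.4). Its 12 subjects are the size of the pilot's TearCare arm (14.2), not the result of a power calculation. The check is mainly textual.

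**1. Does the text permit it?** 24.6 and 24.7 name the Investigator without restriction. 6.4, 6.5 and 13.6 identify that role as co-inventor, performer of the expression and supervisor of all treatments. So yes: it is permitted, though not required.

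**2. Does 11.6 prevent it?** The rule covers follow-up exams. Because 11.5.2 separates exams from questionnaires, the plain wording does not reach SPEED or OSDI. The rule also says nothing about baseline.

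**3. Where would an administrator effect go?** Let *a*(B) and *a*(F) be the effect of the administrator on a subject's score at baseline and at follow-up. Then

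observed change = true change + [*a*(F) − *a*(B)].

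- Coordinator at both visits, same manner: a constant effect cancels.
- Coordinator at baseline, Investigator at follow-up: the whole difference enters the change.
- Investigator at both visits: a constant effect cancels, but any deference that arises because this person has since treated the subject does not.
- If a fraction *p* of subjects have the same one-way switch, the mean moves by *p* times the shift, and more subjects would not shrink it. Switching in both directions equally often would mainly add noise.

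**4. Scale, by illustration only.** The documents give no SD for change in SPEED or OSDI, so shifts are assumed in SD units. The plan does not commit to confidence intervals; one is used here only as a yardstick. At n = 12 a 95% t interval for a mean change has half-width 2.201/√12 = 0.64 SD. Under a constant shift of *b* SD, its coverage is the probability that a noncentral t variable (11 df, noncentrality *b*√12) lies within ±2.201:

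| Assumed shift (SD) | Coverage of nominal 95% interval |
|---|---|
| 0.1 | 94% |
| 0.2 | 90% |
| 0.3 | 84% |
| 0.5 | 65% |

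A small shift is lost in the noise of 12 subjects; a moderate one is not. Nothing in the documents says which applies, and the finding does not depend on this table.

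**The case against.** **The mode of administration is not stated.** Administering a form may mean no more than handing it over and collecting it. If subjects complete the forms unaided, most of the mechanism disappears. This stands, and it is why no size can be claimed. A reader might infer that the Investigator will interview subjects about their symptoms; 24.6 and 24.7 do not say so.

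**11.6 could be read more broadly.** Inclusion criterion 2 uses the term baseline examination for what seems to be the whole visit, so *exams* in 11.6 might be meant to cover everything done at follow-up. That reading is possible, but 11.5.2 points the other way, and 24.6 and 24.7 would still name the Investigator. At the least the sections need aligning.

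**Part of the plan is not visible.** The order of follow-up procedures in 11.6 is redacted and 11.5.3 is not shown. A rule on who gives the questionnaires, or when, may be there. It would still have to be reconciled with the express permission in Appendix A.

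**Another investigator could do it.** Section 15.1 refers to investigators in a form that allows for more than one. Nothing requires that the one who administers the forms be uninvolved in treatment.

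**Little depends on it.** The endpoints are secondary and descriptive, no decision rule uses them, and section 9 openly declines to minimize bias. This limits the severity. Disclosure is not a reason to keep a bias that is easy to avoid, and 11.6 shows that some protection was intended.

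**Conclusion.** The point holds as a minor one. The plan expressly allows an interested treating clinician to administer SPEED and OSDI, two of the three symptom instruments, and allows the administrator to change between baseline and follow-up. Any effect would fall wholly into an uncontrolled mean change. This rests on reading *the Investigator* in Appendix A as the person described in 6.4, and *exams* in 11.6 in the sense used in 11.5.2.

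The size is unknown, and no figure in score points is justified. Two stronger conclusions are tempting but unsupported. One is that the symptom results will be biased: the text permits Investigator administration but does not require it, and the effect may be slight. The other is that changing the administrator would make the symptom results unbiased. Only the administrator's part is removable. Subjects still know that they were treated, and selecting on SPEED of at least 6 still leaves regression to the mean.

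**What to change.** 1. In 24.6 and 24.7 replace "by either the study coordinator or the Investigator" with: *by the study coordinator, in the same way at Baseline and every follow-up visit; the Investigator and any clinician who performed TearCare do not administer it.*
2. Put the same sentence in 24.8, so that SANDE is covered.
3. In 11.6 extend the subject of the sentence to *Follow-up exams and questionnaires*.
4. Keep the completion mode that was used in the pilot (05429), and state it. The visible text does not say what it was. Imposing a new mode could make these subjects' scores less comparable with their earlier ones.

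The cost is protocol wording. The coordinator is already a permitted administrator, so no staff are added. The one practical drawback is that the Investigator could not step in when the coordinator is absent; a trained deputy not involved in treatment could be named for that case.
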